4.3.2.2.5 Confirmatory Safety Phase

The adult dose escalation component of the study is complete at the time of protocol amendment v9.0. Review of the data collected to date with the IDMC led to a decision not to pursue the higher dose level and to commence administration for confirmation in paediatrics at the intermediate dose level. Children are defined as those aged 15 and under in the UK, and 17 and under in the US. These participants in the paediatric confirmation phase are administered the intermediate dose

been shown to be well tolerated in adults. Having identified children who may be willing to participate in the study, the CI will prioritise ATIMP administration to older candidates in the 1st instance. The 1st child administered ATIMP will be monitored for safety for a period of 4 weeks. If there is no adverse event consistent with the above definition of a DLE after 4 weeks, ATIMP will be administered to further children.

In order to fully explore dose levels and make optimal use of the expansion phase of the study, a treatment group randomisation will subsequently occur to either low or intermediate dose; to achieve up to 32 participants receiving intervention at baseline, and up to 16 further participants receiving deferred intervention at 6 months following baseline (control group). The expansion phase will include up to 48 participants in total, who may be adults or children.

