5.4.1.6 Name and Description of Each Non-Investigational Medicinal Product (NIMP)

- 1. Cefuroxime can be administered subconjuctivally at 50mg in 0.5ml normal saline, or 125mg in 1.0mL normal saline according to local practice. or cefazolin at 50 mg/0.5mL or vancomycin at 25 mg/0.5 mL antibiotic given at usual dose at end of surgery (standard (as per British National Formulary) dose as prophylaxis for post-operative infection) or any other antibiotic prescribed as per local hospital practices.
- 2. Long acting steroid in the sub-tenon space following sclerotomy closure according to local guidelines/standard of care.
- 3. Betamethasone can be administered subconjunctivally at 2mg 5mg in 0.5mL, according to local practice. or dexamethasone can be administered subconjunctivally at 1.5mg- 2.0mg in 0.5mL, according to local practice.at end of surgery (standard dose as prophylaxis for post-operative inflammation)) or any other steroid prescribed as per local hospital practices.
- 4. Chloramphenicol 0.5% or ofloxacin (topical antibiotic) 4 times daily for 7 days following ATIMP administration.
- 5. Dexamethasone 0.1% (topical steroid) or topical prednisolone drops 1.0% should be administered 4 times daily for 4 weeks, then 2 times daily for a further 2 weeks (weeks 4 to 6) following ATIMP administration.
 - 3and 4 above will be administered to minimise inflammation and protect against infection postoperatively.

6. Omeprazole:

- In adults 20mg per day for the duration of the steroid treatment
- In children aged up to 16 weighing 5 kg to less than 10 kg (11 lb to less than 22 lb): 5 mg taken once per day for the duration of the steroid treatment
- In children aged up to 16 weighing 10 kg to less than 20 kg (22 lb to less than 44 lb): 10 mg taken once per day for the duration of the steroid treatment
- In children aged up to16 weighing 20 kg (44 lb) or more: 20 mg taken once per day for the duration of the steroid treatment
- 7. Prednisolone or Prednisone (oral steroid) as prophylaxis against potential intraocular immune responses:

For adults 30 mg daily for one week **prior** to ATIMP administration Following the ATIMP administration as follows:

- 60 mg daily in week 1
- 40 mg daily in week 2
- 30 mg daily in week 3
- 20 mg daily in week 4
- 15 mg daily in week 5
- 10 mg daily in week 6
- 5 mg daily in week 7
- 2.5 mg daily in week 8

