Following intraocular administration of ATIMP, the retinal periphery will be examined for any unplanned retinal breaks for appropriate management by retinopexy with or without intraocular tamponade at the discretion of the operating surgeon. Intraocular instruments used subsequent to ATIMP delivery are disposable and will be destroyed after a single use. Sclerotomies may be secured using a vicryl suture. Standard doses of antibiotic and steroid will be administered subconjunctivally as prophylaxis against postoperative infection and inflammation respectively. Bupivacaine will be administered for analgesia.

The surgical procedure may be modified on a case-by-case basis in the interests of safety; any modification will be documented in the operation notes and CRF.

On the basis of experience, it is anticipated that the subretinal ATIMP bleb will resolve spontaneously during the first 48 hours.

Surgery may be performed, as is conventional for intra-ocular procedures, on a day-case basis and participants will be managed subsequently as out-patients, although hospital-based accommodation may be used for convenience.

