Protocol Version 7.0 26 April 2018	To clarify number of visual mobility assessments required To reduce the specificity of anti-biotics that may be prescribed on the trial.
Protocol Version 7.1 19 September 2018 (MEEI Specific)	This amendment was specific to Massachusetts Eye and Ear Institute to include the need for Hepatitis B screening.
Protocol Version 9.0 11 February 2019	To include a randomised component to the expansion phase of the study
	To include further QOL measurement tool To reduce the follow up from 18 to 12 months

	To include an Interim Analysis at 3 and 6 months post treatment for patients in the low/intermediate dose treatment arms of the randomised component of the trial
Protocol Version 10.0 09 August 2019	To amend and clarify the inclusion and exclusion criteria for the trial
	To remove FST at all assessments and to remove ERG at screening to reduce the assessment burden on patients
	To add in Low Luminance Visual Acuity testing
	To include additional Patient Reported Outcomes and to add a Clinician Reported Outcome. To include Treatment Experience interviews.
	To correct minor errors in the Patient Visit Schedule
Protocol v11.0 01 May 2020	Included guidance on the management of patients during COVID 19 pandemic
	Corrected minor errors in the protocol v10.0
	Updated Steroids risks
	Included update local steroid use

10 References

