6.1. Adverse Events

The verbatim terms used in the eCRF by investigators to identify adverse events will be coded using the latest version of the Medical Dictionary for Regulatory Activities (MedDRA) at the time of database lock. Any AE occurring on or after the initial administration of ATIMP within 6 months is considered to be treatment emergent. All reported treatment-emergent adverse events will be included in the analysis. For each adverse event, the number and percentage of subjects who experience at least 1 (one) occurrence of the given event will be summarized by age group, treatment group and overall.

Summary tables will be provided for the frequency and incidence of subjects experiencing the following treatment-emergent adverse events:

- AEs
- Serious AEs (SAEs)
- AEs leading to termination of study participation
- AEs by severity
- AEs by relationship to ATIMP
- AEs by relationship to ATIMP surgery
- Death
- AEs of interest related to ocular inflammation

- Inflammation in cohorts before and after the addition of subTenons triamcinolone injection to the protocol

Summaries of adverse events by system organ class and dictionary-derived (preferred) term will also be provided.

In addition to the summary tables, accompanying listings will be provided for subjects who experience:

- AEs
- SAEs
- AEs leading to termination of study participation
- Death (if any)
- AEs of interest related to ocular inflammation.

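### SAP 6.1 splits inflammation by when sub-Tenon triamcinolone entered the protocol, not by who received it, so the table may misclassify exposure and cannot separate the steroid from phase and calendar time

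*Protocol*

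**What the plan says.** Among the treatment-emergent adverse event summaries, SAP 6.1 lists "Inflammation in cohorts before and after the addition of subTenons triamcinolone injection to the protocol". It does not state which protocol version or date marks the change, and it does not define either group by receipt of the injection. The same section says each adverse event is summarised by age group, treatment group and overall.

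Protocol 5.4.1.6 lists, as a non-investigational product, "Long acting steroid in the sub-tenon space following sclerotomy closure according to local guidelines/standard of care". No agent or dose is given. The next item in that list, the subconjunctival steroid, also allows substitution: "or any other steroid prescribed as per local hospital practices". The operative section (Protocol 5.4.2.2.2) describes only subconjunctival steroid: "Standard doses of antibiotic and steroid will be administered subconjunctivally as prophylaxis against postoperative infection and inflammation respectively".

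On timing, Protocol 4.3.2.2.5 says "The adult dose escalation component of the study is complete at the time of protocol amendment v9.0", and that review of the data with the IDMC "led to a decision not to pursue the higher dose level". The amendment table in Protocol section 9 has "Protocol Version 9.0 11 February 2019" and, at v11.0 of 1 May 2020, an update on local steroid use. SAP section 1 states that the SAP rests on protocol v12.0, which is not among the documents supplied.

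**The concern.** A split by protocol version is a split by calendar time. It measures exposure to the steroid only if nobody before the change received the injection and everybody after it did. The supplied protocol text does not secure either condition. Even with perfect uptake, the two sides would differ in study phase and period, and perhaps in dose mix, in the share of children and in the share of deferred eyes.

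Inflammation is the first ATIMP risk discussed in the protocol (4.1.5.1). Severe unresponsive inflammation is a component of the primary safety outcome, and ocular inflammation is an adverse event of interest in the SAP. A before/after table on this subject invites the reader to judge how much the added steroid helped. As specified, it cannot bear that reading. Other differences between the groups could produce a fall with no steroid effect, and incomplete uptake could hide a real one.

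**Working it through.** The plan states no rate, group size or power for this comparison, so there is no figure to reproduce. The check sets the texts side by side and then shows how each weakness would act, on assumed values.

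**Exposure.** SAP 6.1 names triamcinolone. Protocol 5.4.1.6 names no agent and refers the injection to local practice. Protocol 5.4.2.2.2 does not mention a sub-Tenon injection. On this text, the after group can hold eyes given another drug or none, and the before group can hold eyes injected under local practice.

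**Timing.** Adult escalation, the only phase with the high dose, was complete at v9.0 (11 February 2019). The only logged local-steroid change is v11.0 (1 May 2020), 445 days later. If the injection entered at v9.0 or later, every high-dose eye is in the before group. The log entry names neither the route nor the drug, and the log has no v8 entry, so this is an inference.

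**Dose mix, with no steroid effect.** Pooled before rate = (nH × pH + nL × pL) / (nH + nL); after rate = pL.
- nH: 3 to 6 high-dose eyes (Protocol 4.3.2.2.3; SAP 1.2 reports cohorts of 3 to 4).
- nL: 6 to 49 low- and intermediate-dose eyes in the before group. Six is two cohorts of 3; 49 is 12 escalation + 5 paediatric + 32 immediate expansion eyes at the planned maxima.
- pL = 25%, an assumption borrowed from the 3 of 12 reported for an earlier AAV2/2 trial (Protocol 4.1.5.1). It is not a rate from this trial.
- pH = 50% to 100%, assumed.

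Results:
- nH 3, pH 50%, nL 49: (1.5 + 12.25)/52 = 26.4% v 25%, about 1 point.
- nH 3, pH 100%, nL 17: (3 + 4.25)/20 = 36.3% v 25%, about 11 points.
- nH 6, pH 100%, nL 6: (6 + 1.5)/12 = 62.5% v 25%, about 38 points.

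The result depends heavily on how many expansion eyes were dosed before the change. With assumed rates of 60% (high dose) and 20% (other doses):
- 6 high-dose + 17 other eyes before: (3.6 + 3.4)/23 = 30% v 20%.
- Add all 32 immediate eyes to the before group: (3.6 + 9.8)/55 = 24% v 20%.
- The same with only 3 high-dose eyes: (1.8 + 9.8)/52 = 22% v 20%.

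Within a single dose this component of bias is zero.

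**Uptake.** If risk is otherwise equal, difference shown = true difference × (uptake after − uptake before). Assumed uptakes of 75% after and 25% before show half of any true effect; 50% and 25% show a quarter. The documents give no uptake figure.

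**Other imbalances.** Children also receive intravenous methylprednisolone on the day of surgery (Protocol 5.4.1.6). Deferred eyes are dosed at least 6 months after baseline (SAP 1.2), with COVID-19 delays on top, so they are likely to fall late. SAP section 6 explicitly tabulates only the primary safety outcome for deferred participants after treatment. SAP 6.1 does not say whether their post-dosing events enter this table.

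**The case against.** The strongest reply has five parts.

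First, the SAP follows protocol v12.0, which may name triamcinolone and fix its use. This stands: what is shown about drug and discretion holds only for the supplied text. Even so, SAP 6.1 itself states no cut and does not group by receipt.

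Second, referral to local guidelines may govern agent and dose rather than whether the injection is given; the entry lacks the permissive verb used for the subconjunctival drugs. That is a fair reading. It is why misclassification is possible rather than shown.

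Third, SAP 6.1 already splits by age group and treatment group. If treatment group means dose, high-dose eyes are separated and the dose argument touches only the overall column. This largely stands, but the efficacy sections use treatment group for pooled immediate versus deferred, and say dose level where dose is meant. The split needs confirming.

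Fourth, the table is one descriptive summary with no test and no causal claim. That stands and limits the seriousness.

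Fifth, under local practice, receipt is itself confounded by site and surgeon. That stands too, so the receipt breakdown should be added to the before/after split rather than replace it.

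A reader might infer that all high-dose eyes are known to lie in the before group and that the table will show a spurious fall of about one third. The documents do not support this. The date of the addition is not stated, no high-dose inflammation rate is given, and the one-third figure (30% v 20%) needs assumed rates, the maximum of 6 high-dose eyes and no expansion eyes in the before group. SAP section 3 describes visits up to 12 months at the 2 November 2020 cut-off for those enrolled earlier, which suggests that some expansion eyes may have been dosed before May 2020.

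**Conclusion.** The point holds in limited form. SAP 6.1 groups by the timing of a protocol change that it does not date, and not by exposure. On the supplied protocol text the split may misclassify who had the injection. It is confounded with phase and calendar time, and in any pooled column probably with dose. The table therefore cannot isolate what the steroid did.

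The size cannot be established from the documents. The range of about 1 to 38 points for dose mix, and the loss of half to three quarters of an effect in the uptake examples, rest wholly on assumed rates, splits and uptakes. They show direction and sensitivity and are not expected magnitudes. The dose component also rests on the inferred timing and vanishes if results are shown by dose. The primary safety and efficacy analyses are unaffected. The correction is worth making because it is cheap and bears on a leading safety question.

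**What to change.** In SAP 6.1:
- Keep the before/after table and state the protocol version and date that define the cut.
- Add a breakdown by actual receipt of a sub-Tenon long-acting steroid at surgery (yes/no, and drug).
- Show both splits within low and within intermediate dose, put high-dose and paediatric eyes in separate rows, and include deferred eyes after dosing.
- Label both tables descriptive and non-randomised, noting that receipt may be confounded by site and surgeon.

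Separately, the drug named in SAP 6.1 must be reconciled with the unnamed agent in Protocol 5.4.1.6 and with the operative section, which omits the injection. Which wording is clinically right is not a matter for this point.

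The cost is SAP wording and one extra table. No new data are needed: Protocol 5.4.7 requires all concomitant medication, steroids included, to be recorded from consent; Protocol 5.4.1.6 requires sites to be able to record who received which non-investigational product; and SAP 4.5 already presents corticosteroid use. Grouping by receipt also fits the rule in SAP 2.3.3 that safety is analysed by treatment actually received.

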5.4.2 Protocol Defined Clinical Schedule

5.4.2.1 Baseline Assessments

A detailed assessment of visual function and retinal imaging of both eyes will be performed preoperatively as outlined in Section 5.6 (Table 3: Trial assessments Dose Escalation Phase, Paediatric Dose Confirmation Phase, and Immediate Treatment Arms of Dose Expansion Phase and Table 4: Trial assessments Deferred Treatment Group). For assessments requiring multiple baselines, testing is preferred on separate days within a maximum 3-month period to allow for day-to-day variation and baseline variability for individual participants. However, it is acknowledged that a balance will be achieved between what is pragmatic and appropriate for the different tests on an individual basis. Each set of baseline measurements may take up to 3 days to perform in total in some instances, results for protocol specified baseline tests may be available through a subject's prior participation on the MGT011 RPGR natural history study or as a part of routine clinical examination. As such, if the subject provides informed consent to use the results from the previously conducted tests, then these assessments will not need to be repeated at baseline.

Baseline assessments will be completed as soon as possible after randomisation and will be valid for 3 months⁴. In the deferred treatment group, a day 0 will be applied at the end of baseline assessments and deferred treatment follow up will be calculated from this date.

Up to 10 mL of blood will be collected and to obtain serum samples in order to assess baseline levels of circulating antibodies against AAV serotype 5 and *RPGR* so that immunological responses to vector capsids and transgene product might be determined following vector administration (collectively described as serology in Table 3: Trial assessments). It is anticipated that the majority of participants will have no detectable pre-existing circulating antibodies against AAV5 or *RPGR*. The presence or absence of circulating antibodies will not affect recruitment of the participant. All serology tests will be performed at the Institutional Laboratory in the UK.

⁴ For patients who surgery dates were postponed due to COVID 19 please refer to appendix 1

There is wide variability in the abilities of individual children to perform certain of the proposed investigations; the evaluations for children will be restricted to those tests that individuals are able to perform reliably.

Tests that will be performed in all participants are:

- 1. Serological tests
- 2. Blood pressure
- 3. Haematology
- 4. Biochemistry
- 5. Hepatitis B testing**
- 6. Best corrected visual acuity and low luminance visual acuity
- 7. Contrast sensitivity testing
- 8. Ocular examination
- 9. Static visual field testing
- 10. Spectral-domain optical coherence tomography (SD-OCT)
- 11. Fundus autofluorescence imaging
- 12. Colour fundus photography
- 13. Full-field electroretinography (ERG)
- 14. Pattern electroretinography (PERG)
- 15. Visual mobility assessment
- 16. Patient-Reported Outcome (PRO) questionnaires
- 17. Treatment Experience Interview
 - ** Hepatitis B testing will be performed if required by local practice

Tests that will be performed where possible are:

- 18. Mesopic and scotopic microperimetry
- 19. Detailed psychophysical/colour vision assessments
- 20. Multifocal electroretinography (mfERG)
- 21. Adaptive Optics imaging
- 22. Reading assessment

Further details of clinical assessments can be found in the *RPGR* XLRP study manual. Images taken at all timepoints will be sent for independent reading and analysis at centres in both the UK and US.

With the participant's consent, information collected during their assessments in the format of videos, pictures or similar may be sent to the site where the participant enrolled in the main part of the study, as study records. Copies of this non-identifiable information in the format of videos, pictures or similar may be sent to a third-party provider or to the sponsor and may be used for educational purposes.

(i) Ocular examination and retinal imaging.

Ocular examination using slit lamp biomicroscopy will assess the anatomical integrity of the eyes and allow quantification of intraocular inflammation. During the examination, intraocular pressure will be determined by tonometry.

Retinal imaging includes colour fundus photography, fundus autofluorescence (FAF) imaging, SD-OCT, and adaptive optics (AO) imaging. FAF imaging allows visualisation of the retinal pigment epithelium (RPE) by taking advantage of its intrinsic fluorescence derived from its lipofuscin content. SD-OCT imaging enables measurement of retinal thickness and provides information about the integrity of the layers of the retina. AO imaging provides direct visualization of the photoreceptor mosaics *in vivo*.

(ii) Patient-Reported Outcome (PRO) Assessments.

Patient-reported outcomes should be completed before any other assessments including physician assessments, treatment administration or provision of results in order to reduce the potential to influence the subject's response. The following patient- and clinician-reported outcomes will be assessed as outlined in Section 5.6 - Table 3: Trial assessments (Dose Escalation Phase, Paediatric Dose Confirmation Phase, and Immediate Treatment Arms of Dose Expansion Phase) and Table 4: Trial assessments (Deferred Treatment Group).

Participants will complete age appropriate versions of the Impact of Visual Impairment (IVI) vision-related quality of life (VRQoL) questionnaire, a Low Luminance Questionnaire (LLQ), an age appropriate EQ5D health-related quality of life (HRQoL) questionnaire (EQ-5D-5L or EQ-5D-Y), Patient Global Impression of Severity (PGIS) and Patient Global Impression of Change (PGIC) items. A sample of each of the PROs and instructions for completion are provided in the PRO Completion guide.

Impact of Visual Impairment - Adult (IVI-A) Questionnaire

The IVI-A and IVI-C questionnaires assess vision-related quality of life (VRQoL) in adults and children (respectively) with low vision.

The IVI-A is a 28-item questionnaire comprised of three subscales: (i) mobility & independence, (ii) emotional well-being and (iii) reading & accessing information. (Lamoureux *et al.*, 2006) Response options include 3 and 4 -point Likert Scales (4 items are rated on a 3-point Likert scale: 0 = A lot; 1 = A fair amount; 2 = Not at all; the remaining items are rated on a 4-point Likert scale: 0 = A lot; 1 = A fair amount; 2 = A little; 3 = Not at all). An extra response option 'Don't do this for other reasons' (*excluded from analysis*) is possible for some items. The recall period is the last month. The IVI-A is scored by domain by taking the average of the items in each domain to obtain an IVI raw score (3 IVI raw scores in total). Higher IVI scores reflect greater visual ability/less vision-related quality of life impairment within the subjects.

Impact of Visual Impairment - Child (IVI-C) Questionnaire

The IVI-C is a 24-item questionnaire developed for use in children and adolescents that assesses the impact of vision loss on specific components of VRQoL, including orientation, mobility and social interaction (Cochrane *et al.*, 2008). Subjects are asked to rate the impact of visual impairment on a 5-point Likert scale: *always* (5), *almost always* (4), *sometimes* (3), *almost never* (2), *never* (1), and *no*, *for other reasons*.(Cochrane 2011). The final response is excluded from the analysis. The measure is unidimensional and a global score is calculated ranging from 0-120, with higher scores reflecting less vision impairment/greater vision-related quality of life. Six of the items are reverse scored to reduce response bias.

The Low Luminance Questionnaire (LLQ)

The Low Luminance Questionnaire (LLQ) is a 32-item disease-specific questionnaire for use in eye diseases to assess self-reported visual problems under low luminance and at night. The LLQ consists of six domains including Driving (5 items), Extreme lighting (8 items), Mobility (6 items), Emotional distress (4 items), General dim lighting (6 items), and Peripheral vision (3 items). Response options include 5- and 6-point Likert Scales ranging from "no difficulty at all" or "none of the time" to "stopped doing because of your vision". Two additional response options represent non-applicable or missing data: "stopped for other reasons" and "don't do". The recall period is 'at the present time'. Time to complete the measure is

approximately 5-10 minutes. The instrument is scored by domain, computed by scaling individual items from 0 to 100 and then averaging the individual items for each domain. A higher score reflects higher functional level (Owsley *et al.*, 2006).

EQ-5D Descriptive System

The EuroQol 5-Dimension (EQ-5D) Descriptive System is a standardized measure of health status. Applicable to a wide range of health conditions and treatments, it provides a simple descriptive profile and a single index value for health status that can be used in the clinical and economic evaluation of health care.

The EQ-5D consists of the EQ-5D descriptive system and the EQ visual analogue scale (EQ-VAS). The EQ-5D descriptive system is comprised of 5 items across the following 5 dimensions: mobility, self-care, usual activities, pain/discomfort and anxiety/depression, and can be completed in 2-3 minutes. The EQ-5D-Y uses 3-point Likert response options and has 3 levels of severity for each dimension: No Problems, Some Problems and A Lot of Problems. The EQ-5D-5L uses 5-point Likert response options and has 5 levels of severity: No problems, Slight problems, Moderate problems, Severe problems, and Extreme problems. The recall period is 'Today'. Respondents are asked to indicate their health by placing a cross in the box next to the response that best represents their current health for each of the 5 dimensions. This results in a 1-digit number expressing the level of severity selected for that dimension. The responses for the 5 dimensions can be combined into a 3-digit number (for the EQ-5D-Y) or 5-digit number (for the EQ-5D-5L) describing the respondent's health state (e.g. 11233). The EQ-5D-5L health states, defined by the EQ-5D descriptive system, can be converted into a single index value using country-specific value sets. Index values range from 0 to 1, with higher scores representing better health-related quality of life. The index value facilitates the calculation of quality-adjusted life years (QALYS) that are used to inform economic evaluations of health care interventions. Country-specific value sets are not available for the EQ-5D-Y so an index value cannot be calculated for the child subjects.

The EQ-5D also includes a 20cm visual analog scale (EQ VAS) that has endpoints labelled "best imaginable health state" and "worst imaginable health state" anchored at 100 and 0, respectively. For the EQ-5D-Y, respondents are asked to indicate how they rate their own health by drawing a line from an anchor box to that point on the EQ VAS which best represents their own health on that day. For the EQ-5D-5L, respondents are asked to mark an X at that point on the EQ VAS which best represents their own health

on that day, and entering the number they marked on the line into the box. This can be used as a quantitative measure of health outcome that reflects the patient's own judgement. Completion of the EQ-5D instruments will take approximately 2-3 minutes.

Patient Global Impression of Severity (PGIS)

The Patient Global Impression of Severity (PGIS) is a 1-item questionnaire based on the clinical global impression scale developed by Guy (1976), designed to assess a patient's impression of disease severity. The PGIS asks the patient to select the one response, ranging from 'No Symptoms' to 'Very Severe', that best describes the overall severity of their retinitis pigmentosa 'at this time'

Completion will take approximately 1 minute or less. The PGIS will be assessed at baseline and at 3, 6 and 12 months post-treatment administration (for the low and intermediate-dose group), and at baseline and at 3 and 6 months post-treatment administration (for the deferred treatment group). The PGIS will be evaluated for change over time and used to validate change over time reported on the Patient Global Impression of Change (PGIC) item, to mitigate any potential recall bias on the PGIC.

Patient Global Impression of Change (PGIC)

The Patient Global Impression of Change (PGIC) is a one-item patient-reported measure of perceived change in the patient's health condition following a study/treatment intervention. The PGIC assesses the extent to which a person's health condition has improved, worsened or remained unchanged since the start of their treatment using a scale ranging from 1 = Very much improved to 7 = Very much worse (where 4 = No change). The instructions ask the subject to select the one response that best describes the overall change in their retinitis pigmentosa since treatment was administered. Completion will take approximately 1 minute or less. The PGIC will be assessed at 3, 6 and 12 months post-treatment administration (for the low- and intermediate-dose group), and at 3 and 6 months post treatment administration (for the deferred treatment group).

Clinician Global Impression of Change (CGIC)

The Clinician Global Impression of Change (CGIC) is a generic global measure of change in a patient's health status assessed by a clinician following a study/treatment intervention. The CGIC asks the clinician to rate on a scale from 1 (=very much improved) to 7 (=very much worse) the overall change in the patient's retinitis pigmentosa since treatment was initiated. The CGIC will be assessed at 3, 6 and 12

months post-treatment administration (for the low- and intermediate-dose group), and at 3 and 6 months post treatment administration (for the deferred treatment group).

Treatment Experience Interview

Treatment experience interviews will be administered to all study participants. Subjects in the low- and intermediate dose active treatment group will participate in two interviews: one interview will be conducted at the month 6 / Visit 14 study visit (6 months post-treatment), and the second interview will be conducted at or within 14 days of the month 12/Visit 16 study visit (12 months post-treatment), or upon early withdrawal. The deferred treatment group subjects will participate in one interview at or within 14 days of the month 12 /Visit 16 study visit (6 months post-treatment), or upon early withdrawal. The questions included in the interview will be designed to more fully understand the subject's experience with the study treatment, the aspects of the condition that are most important to them, and the perceived efficacy of the study treatment. The interview will be conducted by telephone and will last 15 to 20 minutes. Subjects will be asked to consent to the treatment experience interview within the study informed consent form (ICF).

A specialist contract research organisation (CRO) will be commissioned to conduct the treatment experience interview sub-study. The study site will facilitate scheduling of the interviews, and the CRO will conduct the interviews by telephone using an experienced qualitative interviewer. For the month 12/ Visit 16 study visit interviews, the interviews may be conducted at the study site during the final study visit, or the subject may participate from their home within 14 days of the final study visit. Interviews will be audio recorded for the purposes of accurate transcription and analysis. The interviews will be transcribed by a third-party transcription agency. The transcripts will have any personally identifying information removed and any errors corrected, after which the audio recording will be permanently deleted by both the CRO and the transcription agency, and the interview transcript will serve as the source document.

The qualitative data collected during the patient treatment experience interviews will be analysed by the CRO and summarised in a final report.

(iii) Functional Assessments

Reading ability including reading acuity, maximum reading rate, and critical print size will be assessed.

Colour vision will be assessed comprehensively using plate tests and computerised tests probing colour discrimination along all 3 axes of colour.

Retinal sensitivity will be determined using static perimetry, and microperimetry (mesopic and scotopic). The retinal locus of fixation will also be determined using microperimetry.

Full-field electroretinography (ERG), pattern ERG (PERG) and multifocal ERG (mfERG) will be performed according to the International Society for Clinical Electrophysiology of Vision (ISCEV) standards to assess both generalised retinal (rod and cone systems) and isolated macular function. Modified ISCEV protocols may be necessary in young children using internationally recognised modified protocols. ERG data will be analysed and interpreted by dedicated full-time Clinical Visual Electrophysiology Consultants with extensive experience and who are directly involved in defining ISCEV standards.

